Once a subject had been screened and qualified for study participation, that subject was enrolled and assigned the next available randomization number. The study randomization table was generated by a third-party statistician. This procedure was used to keep the Study Statistician blinded to subject treatments prior to database lock.

WITHDRAWAL

Subjects enrolled in the study were able to elect to withdraw at any time for any reason. Additionally, subjects were able to have been withdrawn from the study at the request of the Principal Investigator for the following reasons:

1. An adverse event required discontinuation of the study rinse in the judgment of the Principal Investigator or designee
2. Subject refused or failed to comply with the study protocol

3. There was a protocol violation(s) or deviation(s) that compromised the use of the subject's data

All patients withdrawn from the study by request or by the Principal Investigator were to be seen, if they consented, for a close-out evaluation. The reason for withdrawal would be recorded by the Principal Investigator or designee on the End of Study form. Patients who experienced complications and discontinued the study on their own were to be scheduled, if they consented, for an immediate follow-up/close-out examination to determine whether an adverse event was present, and if so, the causation of the adverse event was to be recorded. If treatment was needed for any adverse event causing withdrawal, the subject would be monitored until there was a return to normal conditions. (Every effort would be made to follow up with subjects who withdrew from the study.)

Test Product: ClōSYS® Ultra Sensitive Rinse

Placebo: Oral rinse comprising same ingredients as in test product except for stabilized chlorine dioxide.

Materials:

Sponsor shipped prelabelled 'Oral Rinse A' and 'Oral Rinse X' products to the Test Site. Both products were in 16 oz. size bottle and identical in appearance.

Each subject received the following supplies at Baseline (Visit 1) i.e. supplies for 0-14 days:

- a. 1 bottle (16oz) of either Oral Rinse A or Oral Rinse X))
- b. 35 measuring cups
- c. 1 tube of Crest Cavity Protection Toothpaste, Regular (8.2oz) and
- d. 1 ClōSYS toothbrush

Each subject received the following supplies at Visit 2 i.e. supplies for 15-45 days:

- a. 2 bottles (16oz) of either Oral Rinse A or Oral Rinse X)
- b. 70 measuring cups
- c. 2 tube of Crest Cavity Protection Toothpaste, Regular (8.2oz) and

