Slope of probing depth, time 1 to 3	57	-1.47	0.015	-0.10632	0.323886
Slope of gingivitis index, time 1 to 3	57	-0.99	-0.03	-0.24351	0.221807
Slope of plaque score, time 1 to 3	57	-1.53	-0.045	-0.45254	0.358255
Valid N (listwise)	57				

Global Probing Depths (GPD)

Global probing depth (GPD) collected at the first visit did not differ significantly between groups; control group's (Group A) initial GPD was 2.76 (SEM = 0.092) interval, and 2.68 (0.071) for test group (Group X), a non-significant statistical difference ($p = 0.48$).

Neither did the GPD score differ between final visits of control group (Group A) (GPD = 2.64 (0.130) and test group (Group X) (GPDI = 2.37, (0.166), $t = 1.27$, $df = 55$, $p = 0.28$. Nonetheless, the GPD decreased significantly for control group (Group A), ($p = 0.028$; for X, $p < 0.001$) for both groups, but the group decreases were not significantly different from each other. Both mouthwashes reduced probing depth similarly.

The key signal of treatment effectiveness is a statistically significant treatment-by-time interaction, where improvement over time is greater for one treatment than another. Nearly parallel lines in Figure 2 and statistical testing indicated no appreciable and significant treatment-by-time interaction for GPD (See Figure 2, Figure 3).

Figure 2. Interaction plot showing that group assignment did not interact with time for probing depth.

[figure not shown]

Figure 3. Boxplots of probing depth results from treatment by control group (Group A) and test group (Group X). Probing depth was not affected differentially by the mouthwash treatments. Both conditions reduced probing depth slightly but not statistically significant.

Global Plaque Score

Control group (Group A) and test group (Group X) differed significantly in global plaque score (GPS) at initial assessment, requiring an additional analysis of covariance to confirm that a significant time by treatment interaction was not an artifact from the initial difference in GPS (See interaction plot, Figure 4, detailed in Figure 5). The test group's (Group X) initial average GPS was 3.00 (SEM = 0.071) versus 2.35 (0.097) for the control group (Group A), a significant difference ($t = -5.45$, $df = 50$, $p < 0.001$). At assessment 3, the last observation, the test group's (Group X) GPS (1.57, SEM = 0.110) was significantly lower than that for the control group (Group A); GPS = 1.98 (0.110), $t = 2.633$, $df = 55$, $p = 0.011$.

[figure not shown]

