Transformed Variable: Average outcomes					
Source	Type III Sum of Squares	df	Mean Square	F	Sig.
Intercept	2790.339	1	2790.339	9371.807	0.000
Implant	2.916	1	2.916	9.793	0.002
Measure	13.625	1	13.625	45.761	0.000
Group	1.954	1	1.954	6.562	0.011
Implant * measure	7.58	1	7.58	25.459	0.000
Implant * group	0.018	1	0.018	0.061	0.805
Measure * group	8.331	1	8.331	27.981	0.000
Implant * measure * group	16.127	1	16.127	54.166	0.000
Error	60.738	204	0.298		

Implants and Probing depth

Probing depth scores (PDS) were only collected at initial and last observations visits 1 and 4. At intake, control group (Group A) patients had significantly higher levels of probing depth around implanted teeth (mean = 2.93, SEM = 0.094) than in non-implanted teeth (2.69, 0.063), with $t = 2.31$, $df = 53$, $p = 0.025$. In addition, control group (Group A) implant site probing depth was greater at intake than for test group (Group X) probing depth at implanted sites, 3.40 (0.109) versus 2.45 (0.080) respectively, with $t = 7.07$, $df = 52$, $p < 0.001$.

[figure not shown]
Table 5 represents the results in an overall test of significance with PDS as a dependent variable. There were two notable interactions. One was a time by group interaction, representing that probing depths changed significantly differently over time. Another was a three-way interaction time-by-implant-by-group assignment. The time-by-group interaction was seen before in the PDS score and while significant, the actual difference was less than 1%. The three-way interaction is a false signal in that implant scores probe scores increased slightly in the test group (Group X) and decreased slightly in the control group (Group A) – and neither change was significant.

Probing depth scores for implant and non-implant sites did not change significantly in both groups did not change significantly in both implant and non-implant sites as observed over time for both groups. Figure 8 illustrates the lack of change in implant and non-implant depth scores in either group.

Table 5. Summary results of general linear model of probing depth measures for implant sites over time.

Tests of Within-Subjects Contrasts					
Measure: GGI					
Source	Type III Sum of Squares	df	Mean Square	F	Sig.
Time	15.113	1	15.113	563.159	0.000
Time * implant	1.507	1	1.507	56.172	0.000
Time * group	0.941	1	0.941	35.047	0.000
Time * implant * group	0.001	1	0.001	0.041	0.840
Error(Time)	2.737	102	0.027		

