There is a clear advantage to using ClōSYS® Ultra Sensitive oral rinse treatment (test rinse X) in terms of plaque and gingival index. In addition, ClōSYS® Ultra Sensitive oral rinse (test rinse X) appeared to have a preferential benefit for implant sites, over both control treatment (placebo rinse A) and over non-implant sites. The ClōSYS® Ultra Sensitive rinse (test rinse X) significantly reduced the plaque index and gingival index as compared to initial measures and those in control group (placebo rinse A) ($p < 0.001$). The observation of higher initial gingivitis scores for the ClōSYS® Ultra Sensitive oral rinse (test rinse X) did not affect the superiority of this test group treatment. In controlling for the inequality at baseline, and analysis of covariance showed the reduction of the plaque score remained significantly better in the ClōSYS® Ultra Sensitive oral rinse group (test rinse X) than for the control group (placebo rinse A) ($p < 0.001$). Also, using pre-post difference scores and slopes of the scores over time showed the treatment effect to be robust to the mismatch of initial levels of gingivitis and plaque ($P < 0.001$ for both).

Both groups improved from the use of mouthwashes, but the ClōSYS® Ultra Sensitive oral rinse (test rinse X) improved more and at a faster rate ($p < 0.001$) compared to the control group (placebo rinse A). There was no apparent effect on periodontitis between the two intervals in which it was measured.

Implant sites were significantly more ($p < 0.001$) and faster ($p < 0.001$) improved in the ClōSYS® Ultra Sensitive oral rinse group (test rinse X) than the other non-implanted teeth and in the control group (placebo rinse A).

Both ClōSYS® Ultra Sensitive oral rinse (test rinse X) and placebo rinse (rinse A) tested are safe to oral tissues and did not show any adverse effects.

Both ClōSYS® Ultra Sensitive oral rinse (test rinse X) and placebo rinse (rinse A) tested are safe to oral tissues and do not have any adverse effects.

Signature Page

[name]

Principal Investigator

[name] [name], PhD

REFERENCES

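### Baseline gaps of about 11, 7 and 5 standard errors are not credible as chance after randomisation; the cause is not investigated, and superiority should not be concluded until it is.

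*Combined protocol and SAP*

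**What the plan says.** - **Design.** The Protocol Synopsis describes a double-blind, two-arm trial with 54 patients randomised, 27 per arm. Under Assignment, "The study randomization table was generated by a third-party statistician", and each subject took the next available number. In the Visit 1 procedures the MGI, plaque and BOP gradings are steps 5 to 7 and randomisation is step 11. Probing depth is listed at screening and baseline.
- **Baseline results.** Implants and Probing depth gives control against test as "3.40 (0.109) versus 2.45 (0.080) respectively", with t = 7.07 on 52 df. Global Plaque Score says the groups "differed significantly in global plaque score (GPS) at initial assessment" (3.00 test, 2.35 control, t = -5.45). Global Gingival Index Score gives 2.03 against 1.91, t = -2.89. Table 1 gives implant MGI of 2.82 (test) and 2.06 (control), with no test statistic.
- **Handling.** ANCOVA on the Visit 1 value is reported for global plaque (p < 0.0001) and global gingival index (p = 0.039). For implant MGI, the Figure 9 legend only draws attention to the starting difference.
- **Conclusions.** The higher initial gingivitis in the test arm "did not affect the superiority of this test group treatment". Difference scores and slopes are said to show robustness to unequal starting levels, at P < 0.001 for gingivitis and plaque. A preferential benefit at implant sites is claimed.

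**The concern.** Randomisation after measurement leaves only chance to separate the arms at baseline. When chance is not credible, either the arms were not formed as described or some of the numbers are wrong. ANCOVA adjusts for the measured starting value. It cannot repair biased allocation, and it cannot repair values filed under the wrong measure or arm. Every superiority statement depends on which explanation is true, and no check is reported. Change scores and slopes, which the Conclusions use to show robustness, favour the arm that starts higher, because extreme starting values tend to fall back.

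**Working it through.** **Inputs.** Means and SEMs from Table 1 and the Results text; Table 1 patient numbers are 27 (control, A) and 26 (test, X). Formula: t = (m1 - m2) / sqrt(SEM1² + SEM2²).

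**The document's own figures first.**
- Implant probing depth: (3.40 - 2.447) / sqrt(0.109² + 0.080²) = 0.953 / 0.1352 = 7.05 (printed 7.07).
- Global plaque: (3.00 - 2.35) / sqrt(0.071² + 0.097²) = 0.65 / 0.1202 = 5.41 (printed 5.45).
- Global gingival index: 0.12 / sqrt(0.025² + 0.035²) = 0.12 / 0.0430 = 2.79 (printed 2.89).

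All agree to within rounding of the inputs.

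**Other Table 1 contrasts.**

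| Baseline measure | X | A | t |
|---|---|---|---|
| Implant MGI | 2.82 (0.049) | 2.06 (0.048) | 11.08 |
| Non-implant plaque | 2.99 (0.078) | 2.32 (0.101) | 5.25 |
| Non-implant MGI | 2.01 (0.028) | 1.87 (0.039) | 2.92 |
| Implant plaque | 2.84 (0.057) | 2.77 (0.115) | 0.55 |
| Non-implant probing depth | 2.65 (0.079) | 2.72 (0.099) | 0.55 (A higher) |

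**Chance.** Two-sided p is about 4e-15 for implant MGI, 7e-9 for implant probing depth and 1.5e-6 for global plaque (t = 5.45, 50 df). Multiplied by nine baseline comparisons, the last is 1.4e-5. In 200,000 simulated null randomisations of 27 against 26 (normal data), the largest |t| was 5.29. If the SEMs were per implant, the worst case is full within-patient correlation, which multiplies the variances by 47/27 and 39/26. That leaves t = 8.7 (MGI) and 5.5 (probing depth).

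**A rival figure.** The same section gives Group A implant probing depth as "mean = 2.93, SEM = 0.094". Pooling both arms gives (27 × 3.40 + 26 × 2.447) / 53 = 2.932, SEM 0.0943. So 2.93 is a both-arm mean labelled as Group A and does not displace 3.40. It also suggests that 2.447 was in the analysis file and is not merely a misprint in Table 1.

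**Signs of data or table error.**
- Patient counts: 54 randomised; 27 + 26 = 53 in Table 1; 56 in the 29/56 fraction; 57 in Table 3.
- Group X is given as 26 patients, but 18 + 9 + 2 = 29. Implants are 18 + 18 + 6 = 42 in the text and 39 in Table 1.
- Test-arm global probing depth at baseline is 2.68, above both Table 1 components (2.447 implants, 2.65 teeth). An average over all teeth should normally lie between them if the patients are the same.
- Implants and Plaque says plaque was higher in X at both implant and non-implant sites; Table 1 shows implant plaque balanced.

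**Effect on the claims.**
- Gingival index: the stated falls imply Day 90 values of 2.03 × (1 - 0.273) = 1.476 (X) and 1.91 × (1 - 0.204) = 1.520 (A). The difference in fall is 0.165, of which 0.12 closes the baseline gap and 0.045 is a lower endpoint. With the overall time-3 SD of 0.452, and 27 and 30 patients assumed, the endpoint gap has t of about 0.37.
- Global plaque: X falls 3.00 to 1.57 and A falls 2.35 to 1.98. The difference in fall is 1.43 - 0.37 = 1.06, of which 0.65 closes the gap and 0.41 is a true crossover.
- Implant MGI: reductions of 26% and 19% applied to Table 1 leave X higher (2.09 against 1.67). Reductions of 83% and 57%, stated in the same paragraph, leave X lower (0.48 against 0.89).

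**The case against.** A reader might infer that randomisation must have failed. The documents do not support that. Data error is also possible, and then allocation may have been sound. One candidate is an exchange of the test-implant MGI and probing-depth values. That would put 2.68 back between its components and reduce the two t values to (2.447 - 2.06) / sqrt(0.080² + 0.048²) = 4.1 and (3.40 - 2.82) / sqrt(0.109² + 0.049²) = 4.9. It is unproven: the text repeats 2.45 with its own t, and different patient sets (53 and 57) could also explain the 2.68. Even at 4.1 and 4.9, p is about 2e-4 and 2e-5, and the plaque gap is untouched.

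A reader might also infer that the plaque result is only an artefact of unequal starting levels. That goes too far. The raw Day 90 scores cross over (1.57 against 1.98, p = 0.011), the ANCOVA agrees, and Table 1 implant plaque is balanced. Starting higher does not by itself explain ending lower.

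Three further points stand. Adjusted analyses do exist for the two global indices. No superiority is claimed for probing depth, so that gap bears on allocation and data quality, not on an efficacy claim. Visit 1 includes a data-capture check and the data section mentions inspection and cleaning, so an allocation audit may exist unreported. Variation in the timing of scaling is a weak explanation, because scaling is listed before randomisation.

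**Conclusion.** The concern holds in this form: the baseline gaps in implant MGI (t about 11), implant probing depth (about 7) and global and non-implant plaque (about 5) are not credible as chance, and the gingival index gap (2.89) points the same way. The cause is not identified. Failed allocation, selection after randomisation, and data or table error all remain open; the conflicting counts make data error plausible.

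The claim that the imbalance left superiority unaffected is unsupported, and so is the appeal to change scores and slopes. The implant-benefit claim is weakest, because no baseline-adjusted implant analysis is reported and the stated percentages disagree on which arm ended better. For the primary outcome the adjusted result is p = 0.039; the Conclusions cite only p < 0.001.

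This rests on the printed means and SEMs, on indices taken before assignment as listed, and on t approximations whose far-tail p values show order of magnitude only.

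**What to change.** 1. Before any superiority wording, check each patient's arm against the randomisation list and the label key.
2. Check the macro output against the patient workbooks, above all test-arm implant MGI and probing depth.
3. Reconcile the counts (54, 53, 56, 57 patients; 42 or 39 implants) and correct Table 1 and the text. Report what the audit found.
4. Report baseline-adjusted Day 90 differences for the implant outcomes as well as the global ones. State the gingival index conclusion with its adjusted p = 0.039.
5. Remove the statement that the imbalance did not affect superiority, and the change-score and slope robustness claim.
6. If allocation cannot be confirmed, present the results as a non-randomised comparison.

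The cost is an audit of about 54 records and some re-analysis. The conclusions may weaken.

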The gingivitis index is based on the Gingival Index system,² in this case, the global gingival index is GGI. The GGI was also significantly higher for the test group (Group X) at the initial visit; for the test group (Group X) = 2.03 (0.025) and GGI for the control group (Group A) = 1.91 (0.035), ($t = -2.89$, $df = 55$, $p = 0.006$). Figure 6 illustrates a potential interaction between treatment and time of observation that required statistical consideration and control. Again, GGI for visit 1 was used as a covariate so as not to over-estimate treatment effects on GGI represented in a time-by-treatment interaction. The ANCOVA upheld a statistically significant ($t = 2.12$, $df = 51$, $p = 0.039$) between treatments. Boxplots of the GGI across visits is shown in Figure 7. The test group (Group X) reduction in GGI was 27.3% versus the control group's (Group A) reduction of 20.4%, also statistically significant difference by repeated measures analysis of variance ($F = 8.141$, $df = 1$, $p = 0.0046$).

[figure not shown]

Figure 6. Interaction plot showing group assignment interacting with time on gingival index measures (GGI).

[figure not shown]

Figure 7. Boxplots of gingival index measures comparing treatment control group (Group A) and test group (Group X). Test group (Group X) started with higher gingival index levels. Gingival index decreased more and faster in test group (Group X) than in the control group (Group A), though both decreased significantly.

Differential Effects of Mouthwashes on Implants in Control Group (Group A) and Test Group (Group X)

Of particular interest was the specific effect that control mouthwash (rinse A) and test mouthwash (rinse X) might have on implant and non-implant sites across the three outcomes. Table 4 illustrates the overall study results of treatments and implants on the three outcomes. Probing depth was not different between treatments for implant and non-implant sites. Plaque and gingival indexes were improved significantly under test rinse Treatment (rinse X), with details described in Tables 5, 6, and 7 below. In addition, implant sites improved at a faster rate under test rinse Treatment (rinse X) conditions for both gingivitis and plaque.

Table 4. Omnibus test for main effects and interactions of control mouthwash (rinse A) and test mouthwash (rinse X) on implant and non-implant sites.

Sites of Implants responding differently to treatment					
All outcomes: measures in table					

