Figure 8. No differential effects of mouthwashes on probing depth between implant and non-implant sites. Both groups showed only slight decreases in probing depth. Note that in control condition (rinse A), probing depth was higher for the implant group at baseline.

Implants and Gingival Index

Implant versus normal oral sites also showed a significant main effect ($F = 79.0$, $df = 1$, $p < 0.001$) indicating more and faster gingival index improvement in test group (Group X) for both implant and non-implant sites. Test group (Group X) implants decreased in gingival index scores by 83% while implants in control group (Group A) decreased by 57%. The non-implant sites for control group (Group A) decreased by 23% and for test group (Group X) by 50%. The rate of change was faster for test group (Group X) implants than for control group (Group A) and faster than test group (Group X) non-implant sites. Test Treatment (rinse X) members' implants decrease in gingival index measured 26% versus 19% for those in control group (Group A).

[figure not shown]
Table 6 indicates a strong and statistically significant difference between implant and non-implant sites between and within groups – over time. Figure 9 illustrates the higher gingivitis index in test group (Group X) and greater and faster decrease of gingivitis in test group (Group X).

Table 6. Summary results of general linear model of gingival index measures.

Tests of Between-Subjects Effects

Gingivitis					
Source	Type III Sum of Squares	df	Mean Square	F	Sig.
Intercept	1207.001	1	1207.001	11073.258	0.000
implant	9.949	1	9.949	91.274	0.000
group	9.177	1	9.177	84.187	0.000
implant * group	8.613	1	8.613	79.021	0.000
Error	11.118	102	0.109		

Figure 9. Significant differential effects of mouthwashes on gingival index at implant sites. Both groups showed significant decreases in plaque, but the test group (Group X) reduced gingival index scores more and at a faster rate. Note the difference in gingival index scores at the beginning of the trial.

Implants and Plaque

Plaque scores (PS) for both implant and non-implant plaque scores were higher in the test group (Group X) (2.99 (0.071)) than in the control group (Group A) (2.35 (0.100)) at the first visit, $t = 5.45$, $df = 55$, $p < 0.001$. As with gingival index, PS decreased more for test group (Group X) patients (-0.799 (0.109)) than for control group (Group A) (-0.156 (0.064)) in both implant and non-implant sites, $t = 5.75$, $df = 55$, $p < 0.001$.

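### The implant probing-depth result cannot be verified: text, Table 5 and Figure 8 caption conflict, and the three-way interaction is set aside by a rule that does not test it

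*Combined protocol and SAP*

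**What the plan says.** All places are in Section 11 of the combined protocol and SAP, including its results.

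- *Statistical Evaluation* first names MGI alone for the primary objective. It then lists probing depth with gingival index and plaque as three primary outcomes of a repeated-measures model whose main hypothesis is treatment by time.
- *Global Probing Depths*, on depth averaged over all teeth, says that the plot and testing "indicated no appreciable and significant treatment-by-time interaction for GPD". Table 2 gives p = 0.28 for the slope.
- *Differential Effects of Mouthwashes on Implants* concludes: "Probing depth was not different between treatments for implant and non-implant sites".
- *Implants and Probing depth* points to two interactions as worth noting. On the first: "The time-by-group interaction was seen before in the PDS score and while significant, the actual difference was less than 1" per cent. On the second: "The three-way interaction is a false signal in that implant scores probe scores increased slightly in the test group (Group X"). Placebo implants are said to have become slightly shallower, and the change in each arm is described as non-significant.
- The same section says control patients had greater depth "around implanted teeth (mean = 2.93, SEM = 0.094) than in non-implanted teeth (2.69, 0.063"). It then gives control implants as 3.40 against 2.45 in the test arm.
- The Figure 8 caption says: "Both groups showed only slight decreases in probing depth".
- Table 5 is captioned as the probing-depth model for implant sites, but its measure line reads GGI.
- *Conclusions*: "There was no apparent effect on periodontitis between the two intervals in which it was measured".

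**The concern.** The results section calls the treatment-by-time interaction the key sign that a treatment works. For implant probing depth it names such an interaction, with a direction unfavourable to the test rinse, and discards it on within-arm significance. The implant-by-group terms for gingival index and plaque (Tables 6 and 7) are kept and support a claim of preferential benefit at implant sites. Results for and against the product should be judged by the same rule.

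The reader also cannot recover the right answer. The text has test-arm implants getting deeper, and the Figure 8 caption has both groups getting shallower. The table cited as the test appears to belong to another outcome. The statement that treatments did not differ in probing depth therefore has no visible test behind it.

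**Working it through.** **1. Table 5 as printed.** Error mean square = 2.737/102 = 0.0268.
- Time: 15.113/0.0268 gives F = 563.2 (printed 563.159).
- Time by group: 0.941/0.0268 gives F = 35.07 (printed 35.047).
- Three-way: 0.001/0.0268 gives F = 0.037, or 0.019 to 0.056 over the rounding of 0.001. This is consistent with the printed 0.041, p = 0.840.

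The table is internally sound. The question is which outcome it describes.
- If gingival index, as its measure line says, no test of implant probing depth over time is printed.
- If probing depth, as its caption says, p = 0.840 leaves no three-way interaction to remark on. F = 563 for time and F = 35 for time by group contradict the statement that depth did not change significantly at either type of site.

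The size of the time effect makes the first reading the more likely. Either way something printed is wrong.

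**2. The dismissal rule.** Let the changes at implants in the two arms have opposite signs and sizes z1 and z2 in standard-error units, with equal standard errors (an assumption; none are printed). The between-arm difference in change then has z = (z1 + z2)/√2.
- z1 = z2 = 1.4 (each p = 0.16): z = 2.8/1.414 = 1.98, p = 0.048.
- z1 = z2 = 1.96 (the two-sided 5% limit): z = 2.77, p = 0.006.
- z1 = z2 = 1.0 (each p = 0.32): z = 1.41, p = 0.16.

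Two non-significant changes are thus compatible with a clear interaction or with none. The three-way term also subtracts the same contrast at teeth, but the logic is unchanged.

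**3. The control baseline figures.** Table 1 gives implants 3.40 (SEM 0.109, n = 27) in control and 2.447 (0.080, n = 26) in test, and teeth 2.72 (0.099) and 2.65 (0.079).
- Pooled implants: (27 × 3.40 + 26 × 2.447)/53 = 2.932.
- Pooled teeth: (27 × 2.72 + 26 × 2.65)/53 = 2.686.
- Rebuilding the pooled variance from the within-arm and between-arm sums of squares gives SEMs of 0.0943 and 0.0632.

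These match the printed control values, 2.93 (0.094) and 2.69 (0.063), in mean and SEM. By arm, implant minus tooth is 3.40 − 2.72 = +0.68 in control and 2.447 − 2.65 = −0.20 in test, not +0.24.

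**4. Time by group, and the difference under 1%.** The global section reports no significant interaction; the implant section says one was seen before and was significant. The printed global means give falls of (2.76 − 2.64)/2.76 = 4.3% in control and (2.68 − 2.37)/2.68 = 11.6% in test, a gap of 7.2 points.

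Those means may not be sound, however. Table 3 gives a minimum of 0 for probing depth at time 3 (N = 57, mean 2.50351, SD 0.804056). The mean slope equals half the mean change: (2.50351 − 2.71614)/2 = −0.1063, as printed. The minimum slope of −1.47 is then a fall of 2.94, as from 2.94 to 0. Removing m zeros from the printed mean and SD leaves:

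| m | mean | SD |
|---|---|---|
| 3 | 2.643 | 0.556 |
| 4 | 2.692 | 0.422 |
| 5 | 2.744 | 0.191 |

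Baseline SD is 0.433, so about four zeros fit. Arm sizes for the 57 are not printed.
- Assuming 28 control and 29 test, one zero in control and three in test leave 27 and 26, the Table 1 counts. Means become 2.64 × 28/27 = 2.738 and 2.37 × 29/26 = 2.643, falls of 0.8% and 1.4%, a gap of 0.6 points.
- Assuming 27 and 30, the same removal gives 2.742 and 2.633, falls of 0.7% and 1.7%, a gap of 1.1 points.

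Both use the printed baseline means, which still include the patients removed.

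**5. Baseline imbalance at implants.** 3.40 − 2.45 = 0.95. From the SEMs, t = 0.95/√(0.109² + 0.080²) = 7.03 (printed 7.07). A slight fall from the higher start and a slight rise from the lower one is what regression to the mean would produce.

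**The case against.** The strongest reply is that there may be no interaction to dismiss. The only printed three-way test has p = 0.840, so calling the signal false could be right even if the reason given is wrong. The documents claim no benefit on probing depth, MGI is the outcome first named as primary, and the efficacy conclusions rest on plaque and gingival index. The pooled baseline figures are a labelling slip: the next sentence and Table 1 give the arm values.

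Much of this stands, and it limits the point. A reader might infer that the test rinse deepens probing around implants. The documents do not support that: no size, standard error or valid test is printed for it, and the baseline gap offers another explanation. A reader might also take the global fall in both arms as contradicting a rise at implants. It does not, because the global score averages all teeth in patients with at least 20 natural teeth and mostly one or two implants. Nor should the under-1% statement simply be replaced by 4.3% against 11.6%, since those means may contain visits coded as zero.

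The reply does not rescue the section. If p = 0.840 is for probing depth, the same table contradicts the text on change over time. If it is for gingival index, it says nothing about probing depth.

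**Conclusion.** The implant probing-depth result is wrong as written and cannot be verified. The reason for dismissing the interaction is invalid whatever the data show. The stated rise in the test arm conflicts with the Figure 8 caption, Table 5 conflicts with its own label or with the text, and the two accounts of time by group disagree. The control baseline contrast is overwritten by pooled values (+0.24 printed against +0.68 in Table 1).

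The implant contrast itself cannot be sized: no Day 90 implant depth, change or standard error appears in the text or tables. Figure 8 is not shown in the copy reviewed and may contain them. The comparison between rinses at implants is therefore unresolved, neither shown to be absent nor shown to be adverse.

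The bound on the interaction assumes equal standard errors and a two-sided 5% level, which the documents do not state. The zero-value explanation is an inference from summary statistics and assumed arm sizes, and must be checked in the data.

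**What to change.** - Replace Table 5 with the actual probing-depth model or, if it is that model, correct its measure line and the text that contradicts it.
- Check whether the zero minima at time 3 are missed visits coded as zero. If so, set them to missing and rerun.
- Report implant probing depth by arm at baseline and Day 90, with one value per patient, a baseline-adjusted arm difference and its 95% CI.
- Delete the false-signal argument and judge the interaction by its own estimate and interval.
- Relabel 2.93 and 2.69 as both arms pooled, or replace them with the Table 1 arm values.
- Reconcile the time-by-group statements, the under-1% statement and the Figure 8 caption with the rerun.
- In *Conclusions*, refer to probing depth rather than periodontitis, since depth is what was measured and active periodontitis needing definitive treatment was excluded at entry. State the implant comparison as unresolved unless the rerun settles it.

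The cost is a small rerun on data already held and some rewording. The probing-depth statement may become less favourable to the test rinse.
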